- d. Somerset County Health Department will assist in advertising for the project. Subjects are not being selected based on any specific characteristic(s). Any interested adult in Somerset County can participate. The project is limited to 15 individuals and therefore participation is on a first come-first serve basis.
- e. The project will be advertised through Somerset County Health Department and the surrounding businesses and organizations. All interested adults that reside in Somerset County are welcome to participate if space is still available.

3. Procedures

- a. Participants will be asked to participate in a health screening and preliminary fitness tests after the informed consent has been signed and returned. Participants will be asked to respond with a yes or no to the following questions as a preparticipation and/or health screening tool.
  1. Do you participate in regular exercise?
  2. Has a physician or other qualified health care provider ever diagnosed you with cardiac, peripheral vascular, cerebrovascular disease, or Type 1 or 2 diabetes?

3. Do you have any signs or symptoms suggestive of cardiovascular, renal, or metabolic disease including but not limited to: pain/discomfort in the chest, neck, jaw, or arms; shortness of breath at rest or with mild exertion; dizziness during exercise, ankle edema, palpitations (awareness of rapid beating of the heart) or tachycardia; or unusual fatigue or shortness of breath with usual activities?

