Participants will progress from once to twice a week on non-consecutive days after 2 weeks of participating in the study. This will help participants adapt to the new movement and become familiar with an increase in physical activity. Participants have the option of whether to continue with the study for 12 weeks. Participants will report to Hytche Athletic Complex for a 60-minute combined aerobic and resistance group training session facilitated by the PI. The session will include pre-exercise stretching, an (aerobic) warm-up, weight training, (aerobic) recovery, and a period of post-exercise stretching. The warm-up and recovery will include 10 minutes of steady-state aerobic activity on the indoor or outdoor track. During these periods, walking, jogging, or cardio machines may be used at participant discretion. Static and/or dynamic stretching of each major muscle group will be taught and implemented. The resistance/weight training session will include 8-10 different exercises that target major muscle groups (legs, chest, and back). The time and intensity will progress from one set of 10-15 reps per exercise to three sets of 8-10 reps per exercise. The intensity follows the American College of Sports Medicine guidelines for exercise testing and prescription and will progress from low to moderate intensity (ACSM, 2021). Abdominal and low-back exercises will also be incorporated throughout the weight training portion to promote muscular balance. Participants can ask for an alternative method and/or not to participate in one or all of the exercises after they are demonstrated and explained.

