- b. To minimize cardiovascular and muscular fatigue (DOMS) associated with a new mode of activity/bodily movements, participants can withdraw from the activity and/or exercise session at any time. Also, weeks one and two of the study will only use the participant's body weight to allow for a gradual adaptation of new activity/bodily movements. Participants will also be introduced to the new movement before it is introduced as a part of the program. To minimize discomfort associated with an increase in heart rate, participants will be reminded that they can take rest as needed and that they may also withdraw from the session and/or study whenever they choose. To minimize the effect that resistance training can have on blood pressure, the National Strength and Conditioning Association (NSCA) recommends aerobic, steady-state activity, such as walking proceed resistance training sessions. A 10-minute recovery period is a part of the 60-minute training session. During this time participants will walk or ride a non-weight bearing cardio machine.

Apparently healthy participants and/or those participants cleared by a physician to participate, still may be terminated by the principal investigator if participants' ratings of perceived exertion with an activity is too high. The Borg Rating of Perceived Exertion Scale is a scale used to monitor intensity during exercise. This scale has since been updated to the revised category ratio scale, CR10. The scale originally went from 6 to 20 with 6 being no exertion at all and 20 being maximal exertion. The revised/updated scale goes from 0 to 10. The scales correlate with exercise heart rates. Three revised CR10

color-coded posters will be hung around the dance studio. Participants will be asked to rate themselves throughout each 60-minute session. A detailed description of the scales is included with the IRB materials that are attached.

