- c. The participants will be the direct beneficiaries of this study. Currently, there are limited to no opportunities for community residents to be physically active. Somerset County has the highest physical inactivity and physical health levels among surrounding counties. Expected benefits include improved weight maintenance, body composition, and health-related physical fitness. Participants can also expect to learn proper form and technique with flexibility, calisthenics, and resistance training exercises. Participants will also gain an understanding of how they can maintain physical activity levels despite the conclusion of the intervention. This study will contribute to existing research on health-focused community-health intervention programs in rural areas.
- d. Since the study is open to Somerset County community residents, the benefits will be distributed fairly. Participants will engage in the same program and receive the same services. It must be noted that participants may receive different levels of benefits based on individual motivation, consistency, and initial starting point in regards to physical activity. Children are not included in this study because children require a different training regime due to physical and neurological limitations associated with participation in a training session. Additionally, it is not appropriate for pregnant women to participate in this program. It would be difficult to assess changes in body composition and components of physical fitness as pregnant women undergo physiological changes that are relevant to being pregnant. For example, pregnant women may have a higher resting heart rate, lower aerobic capacity and/or exercise tolerance, and higher body fat levels. The purpose of this program contradicts some of the changes expected to take place with pregnant women and therefore the risks associated with their participation outweigh the potential benefits.

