## 5. Privacy/Confidentiality

- a. Confidentiality of subjects' identification and information collected will be maintained on a password-protected laptop loaned by the principal investigator by UMES. The laptop is kept in locked office. The principal investigator is the only individual who will have access to the computer. The middle name of the subject will be used for assessing before and after intervention changes. The participant's middle name will be used to generate a pseudonym. The key/code for the pseudonym will be kept on the same file that data is being stored on. The principal investigator is the only individual who will see individual test results. The participant may be given their own results after completion of the assessments for personal use. The principal investigator will not share individual test results with anyone other than with the participant. Before and after test results will be used for research purposes to determine effectiveness of the intervention however, the middle names of the participants will be removed from the data/file since it will no longer be needed. The key/code will be deleted.
- b. Information collected from the participants will not be shared with other participants. The principal investigator is the only individual who will have access to the information collected. If participants would like to know the information being collected from

him/herself, this information will be shared with the participant. Information collected from each participant will be done on an individual basis in the exercise science lab. The exercise science lab is located in the Department of Kinesiology in Hytche Athletic Complex on UMES campus. The PI will put the data into an excel spreadsheet. The PI will ask each participant if he/she would like a copy. Each individual session for the collection of measurements and assessments will be by appointment only. The information collected from the participants will be stored on a password protected laptop that only the principal investigator has access to. The participant's middle name will be used to identify their pseudonym until the conclusion of the intervention. Once the intervention ends, the participant's middle name and pseudonym will be deleted from the key/file and numbers will replace the names.

6. Informed Consent

- a. See attachment.

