- b. Interested participants may call, email, or access the google form through the link provided by the principal investigator on the invitation to participate. Once the participant expresses interest by providing their contact information, an individual appointment will be scheduled to explain the study and the procedures. The informed consent, ACSM screening algorithm, PARQ+, and supplemental informed consents, if applicable, will be explained to the participant. The participant will be given time to ask questions. If the participant is still interested in participating, he/she will be asked to sign the documents. At these individual meetings, each participant will be provided a copy of the informed consent for him/her to keep.
- c. The readability report for the informed consent was over 12th grade with an age of 19 to 20 years old.

7. Research Plan for Collection, Storage, and Analysis of Data

- a. Data will be collected using a tape measure and a bioelectrical impedance analysis (BIA) device. Participants will be asked to complete a fitness test which includes a bench press, vertical jump, pushup, curl up, and either a 1-mile walk or 1.5 run/walk test. Data collected is what the participant completes through counting or by using a stopwatch. Participants can choose not to complete some or all of the fitness test. The PI is responsible for supervising all sessions. The PI is certified through both national certifying organizations, the National Strength and Conditioning Association and the American College of Sports Medicine, for exercise program design, implementation, and safety. The PI is required to maintain three certifications through pre-approved continuing education through the certifying organization as well as maintaining a current Cardiopulmonary Resuscitation (CPR) and Automated External Defibrillator (AED) certification. Additionally, there is a licensed athletic trainer working in Hytche Athletic Complex.
- b. Data will be stored in an excel spreadsheet on a password-protected laptop loaned to the principal investigator from the university. The PI is the only individual who has access to the laptop.

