- c. Data will be analyzed for the mean and standard deviation of pre and post individual assessment data as a result of the intervention sessions. ANOVA with significance set at  $p<0.05$  will be used to determine the significance of the change in body weight, composition, waist circumference, and measures of fitness that may or may not have occurred. The mean and standard deviation of scores, pre and post, will be calculated and reported.
- d. The PI is the only individual who will have access to the data. Participants may request a copy of personal measurements/assessments prior to the conclusion of the study as pseudonyms may be replaced with numbers.
- e. The data will be kept for three years at the conclusion of the study.
- f. After the three-year period, the file will be deleted from the computer and the deleted folder will be emptied.

8. Conflict of Interest

- a. Potential conflict of interest includes receiving a grant from Somerset County Health Department (SCHD) for the development and implementation of a health intervention program for adults in Somerset County. This research effort and collection of data is not a condition of the funding received. This project may be carried out without intentions of a publication and/or presentation however, it has the potential to contribute to a body of knowledge on community health interventions and how they may be implemented. Additionally, results obtained from this project will be useful in applying for additional funding opportunities that will benefit the surrounding community. A narrative will be shared with SCHD at the completion of the project however, no raw data will be shared. The narrative will include results from the data analysis. The funding covers the equipment that will be needed, supplies for the participants, and salary. Equipment will include items such as the most accurate BIA home device, medicine/physio balls, exercise mats, stretching bands, and dumbbells. Supplies will include items such as hand towels, water, sanitizing wipes, and post-session snacks. Salary will be given to the PI for development and implementation of the intervention. This conflict will not affect the level of risk to the study participants and will be disclosed in the informed consent. Additionally, disclosure of this conflict of interest will be included in publications and/or presentations of the study results.

9. HIPPA Compliance

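### Sections 5a and 7c word the before/after change as the intervention's effect, but with one arm, one baseline and no comparator the analysis can show only that scores changed

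*Combined protocol and SAP*

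**What the plan says.** Two sentences in the combined protocol and SAP attach a causal meaning to the before/after data.

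- Section 5 (Privacy/Confidentiality), item a: "Before and after test results will be used for research purposes to determine effectiveness of the intervention".
- Section 7 (Research Plan for Collection, Storage, and Analysis of Data), item c, first sentence, which describes means and standard deviations of "pre and post individual assessment data as a result of the intervention sessions".

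The next sentence of 7c sets out the test, an ANOVA at p<0.05, and is neutral. It addresses "the significance of the change in body weight, composition, waist circumference, and measures of fitness that may or may not have occurred".

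The design behind these sentences is as follows.

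- One arm. Section 4, item d: "Participants will engage in the same program and receive the same services".
- One baseline and one post measurement. Section 3, item a, has the fitness tests done once in the week before the program, BIA, weight and waist taken before and after, and the whole set repeated at the end.
- Size. Section 2, item d: "The project is limited to 15 individuals".
- Completion is voluntary. Section 3, item a: "Participants have the option of whether to continue with the study for 12 weeks". Section 7, item a: "Participants can choose not to complete some or all of the fitness test".

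No section describes a control group, wait-list, run-in, repeated baseline or external comparator, and none states a limitation on attribution.

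**The concern.** Determining effectiveness means separating what the sessions did from what would have happened anyway. Nothing in this design shows what would have happened anyway, so the stated inference goes beyond what the data can deliver.

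The wording matters because of where the results go. Section 8, item a, says the analysis results will appear in a narrative for the funder, which receives no raw data, and that they are expected to help in later funding applications. If the 5a wording, or the opening of 7c, is carried into that narrative, an observed change will read as a demonstrated effect. Section 7c also does not say who is analysed and asks for no counts, so a reader could not tell how many of those who started stand behind each result.

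**Working it through.** **Step 1. What the test addresses.** The plan states no effect size, SD, power or expected change, so there is no figure to reproduce. Section 7c does not name the ANOVA model; I assume a within-subject ANOVA on two time points, which is the paired t-test (F = t²). Write the mean change as

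mean change = program effect + shift from any other cause.

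The test's null hypothesis is that this sum is zero. One arm with one baseline gives one estimate for two unknowns, so the parts cannot be separated. This holds at any sample size.

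**Step 2. Which other causes the documents leave open.**

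- *Test familiarity (fitness tests only).* The same tests are repeated. Section 3, item b, provides demonstrations and up to three jumps, which reduces this but does not remove it.
- *Drift over about 12 weeks.* It could go either way; the documents give neither size nor sign.
- *Other behaviour change.* No section records diet or outside activity during the program.
- *Selective completion.* Continuing is optional and fitness tests may be skipped (sections 3a and 7a).

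**Step 3. Illustration of a shift. Every shift is assumed.** Units are SDs of the individual change scores. With n pairs and true mean change d, the chance of a significant favourable result is P(T > t(0.975, n−1)), where T is noncentral t with n−1 degrees of freedom and noncentrality d√n. I take n = 15, the enrolment cap, with everyone completing. The critical value is 2.145, so the smallest significant change is 2.145/√15 = 0.554 SD. With a program effect of zero:

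| Assumed shift (SD) | Noncentrality | Significant benefit |
|---|---|---|
| 0 | 0 | 2.5% |
| 0.3 | 0.3 × 3.873 = 1.162 | 19.0% |
| 0.5 | 0.5 × 3.873 = 1.936 | 43.8% |

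The shift can also act against the program. A true effect of 0.8 SD is detected in 82.1% of studies. With an adverse shift of 0.3 SD the net change is 0.8 − 0.3 = 0.5 SD, and detection falls to 43.8%.

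**Step 4. Is the small sample the cause?** With 10 pairs instead of 15, the 0.3 and 0.5 SD shifts give a significant benefit in 13.4% and 29.3% of studies, against 19.0% and 43.8%. More participants make a non-program shift more likely to reach significance, not less. Sample size governs precision; the comparator governs attribution.

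**Step 5. Illustration of selective completion. All inputs are assumed.** Fifteen start, the true mean change is zero, and the 10 with the highest completion score have both values. That score correlates ρ with change. The expected mean of the top 10 of 15 standard normal values is about 0.517, so the completers' mean is 0.517ρ. In 400,000 simulated studies:

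| ρ | Completers' mean (SD) | Significant benefit |
|---|---|---|
| 0 | 0 | 2.5% |
| 0.3 | 0.16 | 7% |
| 0.5 | 0.26 | 13% |
| 0.7 | 0.36 | 23% |

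The documents do not say how many will complete or whether completion relates to change.

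**The case against.** The strongest reply is that the plan hardly makes this claim. The 5a sentence is a passing remark in a privacy section, explaining why results are kept once names are removed. In 7c the phrase about the sessions attaches loosely to the data, and the sentence that sets out the test is neutral. Nothing shows that the funder narrative will use the 5a wording. The limitation is common to any uncontrolled community program, and the illustrative percentages rest wholly on assumed inputs.

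Much of this stands. The percentages say nothing specific about this trial, and harm through the narrative is a risk, not a stated plan. But the neutral sentence in 7c leaves open whether a change occurred; it does not address what caused it. The only statement of what the before/after results are for is the one in 5a, and no section qualifies it.

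A reader might infer more than the documents support:

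- *That 15 participants is the reason the effect cannot be established.* It is not (Step 4).
- *That the result will be biased in the program's favour.* The documents give no direction.
- *That the Bod Pod amendment leaves the pre/post measure of composition or weight unclear.* It does not. Sections 3a and 9a set BIA and body weight as the measures at both ends, and the amendment presents the Bod Pod as an additional use.
- *That participants stopped for high perceived exertion (section 4b) drop out of the analysis.* That text does not say their post-test is lost, so I do not rely on it.

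**Conclusion.** The concern holds as a matter of stated inference. Sections 5a and 7c attribute to the intervention what a single-arm, single-baseline comparison can only describe. The conclusion rests on the design as written and needs no numerical assumption.

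Its size in this trial cannot be estimated from the documents. The figures of 19% and 44%, against 2.5% by chance, show only how an assumed shift of 0.3 or 0.5 SD would pass the test with 15 pairs and a within-subject ANOVA; they are not error rates for this study. The pre/post data remain useful as description, and neither the test nor the design has to change for that use.

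**What to change.** 1. In sections 5a and 7c and in the funder narrative, replace the effectiveness and as-a-result-of wording with *change observed over the 12-week program, without a control group*, and make no causal claim.
2. As a supporting addition to 7c, report for each outcome how many participants started and how many have both a pre and a post value, and state that the ANOVA uses the latter. This shows the extent of selective completion; it does not remove it.

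The cost is a few words in two sections and the narrative, plus two counts per outcome from the existing spreadsheet. No measurement is added and the ANOVA is unchanged. The downside is a less favourable headline, with losses made visible.

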An ACSM screening algorithm and the PARQ+ will be used to determine if a participant needs medical clearance prior to participation in the preliminary fitness tests which is completed a week before the program begins. The preliminary fitness tests will include the curl up, the pushup, bench press, vertical jump, and the Rockport 1-mile or 1.5 mile walk test. The purpose of the fitness test is to acquire baseline data about physical fitness levels before implementation of the intervention. The preliminary fitness test will not be used to determine if an individual can or cannot participate. Participants will complete a Bio-electrical Impedance Analysis (BIA), body weight, and waist circumference measurements before and after the study. The BIA will be used to determine percent body fat, skeletal muscle, and body mass index. The PI will program the BIA device. The participant will be asked to step on a scale and hold the handle of the BIA device. The participant will be asked to hold the BIA device for up to 5 seconds until the device completes the scan. The weight of the BIA device is approximately 12 ounces. BIA devices are available for the public and may be purchased by the public. To measure the participant’s waist circumference, a tape measure will be placed around the participant’s waist on the outside of their shirt. The participant will be asked to identify where their belly button is and the participant will wrap the tape measure around their waist. One inch below the participant’s belly button is where the participant will be asked to place the tape measure. The BIA and waist circumference measurements will be conducted in the exercise science lab located in the Department of Kinesiology in Hytche Athletic Complex on UMES campus.

These data collected from participants will be recorded and stored on a password protected university-owned laptop. The participant’s middle name will be used as an

identifier until post assessments are complete. Post assessments are completed at the end of the program and will include all of the preliminary assessments.

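### Section 7c does not state that its ANOVA is within-person, plans no precision for the pre-to-post change, and does not tie the pre and post means to the same people

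*Combined protocol and SAP*

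**What the plan says.** The analysis plan is section 7c of the combined protocol and SAP. It plans the "mean and standard deviation of pre and post individual assessment data" and an ANOVA at p<0.05, which "will be used to determine the significance of the change in body weight, composition, waist circumference, and measures of fitness". It closes with: "The mean and standard deviation of scores, pre and post, will be calculated and reported". It names no factor, subject term, repeated-measures or paired form, change score, confidence interval or analysis set.

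The design around it is one group measured twice:

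- **Size.** Section 2d: "The project is limited to 15 individuals".
- **Assessments.** Section 3a: "Post assessments are completed at the end of the program and will include all of the preliminary assessments".
- **Linkage.** Section 3a keeps the middle name as an "identifier until post assessments are complete". Section 5a says that this name serves to compare results before and after the intervention.
- **Missing values.** Section 3a: "Participants have the option of whether to continue with the study for 12 weeks". Section 7a lets people decline any part of the fitness test.
- **Reporting.** Section 8a promises the funder a narrative without raw data: "The narrative will include results from the data analysis".

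**The concern.** When the same people are measured twice, the evidence lies in each person's change. A repeated-measures ANOVA with a subject term removes the stable differences between people. A single-factor ANOVA with time as its only factor leaves them in the error term. The wording of 7c would be satisfied by either.

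Two further gaps do not depend on that choice. First, the planned summaries are a mean and SD at each time. They allow a subtraction but do not show how precisely the change is known. Section 5a says the before and after results will be used to judge whether the intervention works, and section 8a expects them to support further funding applications, so precision is what those readers need. Second, 7c does not say whose scores enter each mean. If the pre mean uses everyone and the post mean only those who came back, part of the difference may come from who left.

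**Working it through.** The documents contain no power, precision or sample-size figure, so there is nothing to reproduce.

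**Inputs.** From the documents: n=15 (the cap in section 2d) and a 0.05 level (section 7c). Assumed, because the documents give none: two-sided tests, equal pre and post SDs, pre-post correlation r of 0.5, 0.80 or 0.95, and the size of the change. Everything is in units of the outcome SD.

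**1. Precision of the change.** SD of change = sqrt(2(1-r)). The 95% half-width is t(0.975, 14) x SD of change / sqrt(15), with t = 2.145. For a difference in means of 0.25 SD:

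| r | SD of change | Half-width | Paired 95% CI | Paired p |
|---|---|---|---|---|
| 0.95 | 0.316 | 0.175 | 0.07 to 0.43 | 0.008 |
| 0.80 | 0.632 | 0.350 | -0.10 to 0.60 | 0.15 |
| 0.5 | 1.000 | 0.554 | -0.30 to 0.80 | 0.35 |

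The pre and post means and SDs are identical in all three rows. The p-values belong to the paired test only. Single-factor ANOVA on the same data gives t = 0.25 / sqrt(2/15) = 0.25 / 0.365 = 0.68 on 28 degrees of freedom, p = 0.50, whatever r is.

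A bare statement of significance adds little. If the test is known to be paired, p<0.05 for this difference says only that the SD of change was below 0.25 x sqrt(15) / 2.145 = 0.45, that is, r above 1 - 0.451^2 / 2 = 0.90.

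**2. What the choice of ANOVA would do.** The single-factor standard error is sqrt(2/15) = 0.365. The actual standard error of the mean change is sqrt(2(1-r)/15), which is 0.163 at r=0.80. The ratio is 1/sqrt(1-r): 1.4 at r=0.5, 2.2 at 0.80 and 4.5 at 0.95. Paired power comes from the noncentral t with noncentrality change x sqrt(15) / sqrt(2(1-r)). Single-factor power comes from simulation, 200,000 runs per cell.

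| r | 0.40 SD: paired | 0.40 SD: single-factor | 1.0 SD: paired | 1.0 SD: single-factor |
|---|---|---|---|---|
| 0.5 | 30% | 11% | 95% | 82% |
| 0.80 | 63% | 5% | 100% | 90% |
| 0.95 | 99.5% | 1.4% | 100% | 95% |

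With no true change, the single-factor test rejects in about 0.8% of trials at r=0.5 and 0.02% at r=0.80, against a nominal 5%. It is conservative. At r=0.5, power for a 0.40 SD change is low with either test, because n is at most 15.

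**3. Means from different people.** As an illustration only, suppose 3 of 15 leave, those 3 averaged 1 SD above the baseline mean, and nobody's score changes. The remaining 12 average -3 x 1 / 12 = -0.25 SD. The pre mean of 15 and the post mean of 12 then differ by 0.25 SD with no change in anyone. The size follows entirely from the assumed leavers. The point is only that 7c does not exclude such a comparison.

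**The case against.** The strongest reply is that a paired analysis is plainly meant. Section 7c speaks of individual data and of change, section 3a holds the identifier until the second assessment, and section 5a ties it to the before-and-after comparison. This largely stands. A reader might infer from the bare word ANOVA that an unpaired test will be run, and the documents do not support that. They show only that 7c leaves the form open, so the power contrasts apply only if the less natural reading is followed.

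Three other stronger readings also fail:

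- **False positives.** A reader might infer that the wrong ANOVA would produce spurious success. With positive correlation it does the opposite.
- **A biased test.** A reader might infer that unmatched people distort the significance result whichever ANOVA is run. A complete-case repeated-measures test uses only people with both values, so under that test the mismatch touches the descriptive means alone.
- **No estimate at all.** A reader might infer that the size of the change goes unreported. Where the same people are in both means, their difference is the mean within-person change. What is missing is its precision and a matching rule.

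It is also fair to say that 7c does not forbid change scores or exact p-values. An exact paired p, with the number of pairs and matched means, would let a reader recover the interval. But 7c commits only to a 0.05 threshold, and section 8a promises results without saying which.

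**Conclusion.** The point holds as a gap in specification and reporting that should be fixed. It does not show that an unsound test has been chosen. Followed as written, 7c can produce a report in which the same two means and SDs are compatible with a clear change or with none: a 0.25 SD difference has a paired interval of 0.07 to 0.43 at r=0.95 and -0.30 to 0.80 at r=0.5. That gap, and the freedom to report means for different people, exist whichever ANOVA is run. The loss of power (about 63% to 5% at r=0.80 and a 0.40 SD change) is conditional on a single-factor analysis, and it errs towards missing a real change. All sizes rest on n=15, equal SDs, two-sided tests and assumed correlations and changes. That 7c omits the test form, the precision and the matching rule does not rest on those assumptions.

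**What to change.** Replace the analysis sentences in 7c with these commitments:

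- For each outcome with both a pre and a post value from the same test, use a paired t-test or, equivalently at two time points, repeated-measures ANOVA with a subject term. The same-test condition matters because section 7a offers two distances for the walk or run, and because the amendment schedules the Bod Pod only at weeks 8 and 12, so it has no pre value.
- Report the number of pairs, mean change, SD of change and 95% CI, with the pre and post means for those same people.
- Show the number and baseline values of people without a post value.
- State as a limitation, without numerical bias figures, that complete pairs can still be biased by selective leaving and by regression to the mean.

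The cost is three or four sentences. The data and spreadsheet stay the same, with no added participants or visits. The downside is fewer people per analysis when post values are missing. At an assumed r=0.80 the 95% half-width is 0.35 SD with 15 pairs and 2.262 x 0.632 / sqrt(10) = 0.45 SD with 10.
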